We estimated the baseline mortality using the prospective ANZ observational study data [3]. Over 5 weeks in 2008, 757 patients were recruited. The exclusion criteria of TRANSFUSE leaves 45% recruitable patients. These patients had a hospital mortality of 25% and we conservatively estimate 90-day mortality to be 28%. Our sample size calculation is based on a 15% relative decrease in 90-day mortality, or an absolute decrease of 4.2% from 28% to 23.8%. This effect size would be clinically highly relevant (Number needed to treat to save one life [NNT]=24). This relative decrease is much less than observed in the Koch study (30% RRR) [28], and in our observational study where we found a mortality of 21.3% in the older three quartile versus 13.2% in the freshest quartile (38% RRR) [3]. With a type I error of 0.05 and a type II error of 0.1 (power 90%), the required patient number is 2332 per group. According to our previous studies [54, 55], loss to follow up should not exceed 5%, giving an accurate number of 4898 patients which has been rounded up to 5000 patients.

Statistical and analytical plan

This study will be analysed on an intention-to-treat basis. Analysis will primarily be conducted using SAS version 9.2. (SAS Institute Inc., Cary, NC USA). Baseline comparisons will be performed using chi-square tests for equal proportion, student t-tests for continuously normally distributed variables and Wilcoxon rank sum tests otherwise. The primary outcome, 90 day all-cause mortality will be analysed using a Chi-square test statistic, with results reported as frequencies and percentages per arm. Adjustment for strata (centre) will be made using logistic regression for binomial outcomes and Cox Proportional Hazards regression for time to event data with results reported as Odds Ratios (95% CI) or Hazard ratios (95% CI) respectively. In the unlikely event that baseline imbalances are found to exist between treatment groups, sensitivity analysis will be performed with imbalanced variables included as covariates. A two-sided p-value of 0.05 will be considered to be statistically significant. Additionally a per protocol analysis will be undertaken to account for patients with alloantibodies for whom freshest blood is unavailable. A detailed statistical analysis plan will be published prior to analysis being performed.

Subgroup analyses

A priori subgroup analyses will include:

- Group O versus non group O
- Illness severity according to APACHE III and SOFA scores

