Data will be assessed for normality and log-transformed where appropriate. Univariate analysis will be conducted using student t-tests, chi-square test for equal proportion or non-parametric tests where appropriate. Multivariate analysis will be performed adjusting for baseline imbalances and known covariates and confounders. Multiple logistic regression will be used for AKI as a binomial outcome. Linear regression will be used for analysis of continuous outcomes. The difference between groups for daily serum creatinine will be determined using generalised linear modelling fitting main effect for group and time and an interaction between group and time to determine if the two groups behave differently over time. A two-sided p-value of 0.05 will be considered to be statistically significant. All data will be analysed using Intercooled Stata, version 9 and above (Statacorp, College Station, Tx, USA).

Publication

The study will be conducted in the name of Monash University on behalf of the TRANSFUSE investigators. Authorship will be under the names of the sub-study investigators on behalf of the TRANSFUSE investigators. Publication of results will be embargoed until publication of the main study results unless specific permission for early publication is given by the TRANSFUSE management committee.

REFERENCES

1. Corwin, H.L., et al., *The CRIT Study: Anemia and blood transfusion in the critically ill--current clinical practice in the United States*. Crit Care Med, 2004. **32**(1): p. 39-52.
2. Vincent, J.L., et al., *Anemia and blood transfusion in critically ill patients*. Jama, 2002. **288**(12): p. 1499-507.
3. Pettila, V., et al., *Age of red blood cells and mortality in the critically ill*. Crit Care, 2011. **15**(2): p. R116.
4. Investigators, T.B.O.S., *Transfusion practice and guidelines in Australian and New Zealand intensive care units*. Intensive Care Med, 2010. **36**: p. 1138-1146.
5. Service, A.R.C.B., *Annual Report*, h.w.d.c.a.f.p.B.S.a. report, Editor 2007 to 2010.
6. Hebert, P.C., et al., *A multicenter, randomized, controlled clinical trial of transfusion requirements in critical care*. Transfusion Requirements in Critical Care Investigators, Canadian Critical Care Trials Group. N Engl J Med, 1999. **340**(6): p. 409-17.
7. Marik, P.E. and H.L. Corwin, *Efficacy of red blood cell transfusion in the critically ill: a systematic review of the literature*. Crit Care Med, 2008. **36**(9): p. 2667-74.

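### The covariates for the mortality sensitivity analysis are chosen by observed baseline imbalance, which is undefined and ignores prognostic strength; a list fixed in advance would be a better check

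*Combined protocol and SAP*

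**What the plan says.** The relevant text is in Statistical Considerations, under Statistical and analytical plan.

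- Baseline testing: "Baseline comparisons will be performed using chi-square tests for equal proportion, student t-tests for continuously normally distributed variables and Wilcoxon rank sum tests otherwise".
- Use of the result: "In the unlikely event that baseline imbalances are found to exist between treatment groups, sensitivity analysis will be performed with imbalanced variables" entered as covariates.
- The only threshold, given in the sentence after that: "A two-sided p-value of 0.05 will be considered to be statistically significant". It is a general statement and is not tied to the baseline tests.
- Primary analysis: "The primary outcome, 90 day all-cause mortality will be analysed using a Chi-square test statistic".
- The only adjustment named in advance: "Adjustment for strata (centre) will be made using logistic regression for binomial outcomes", with Cox regression for time-to-event data.

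APACHE III and SOFA are listed under Data variables collected, but in the analysis text they appear only under Subgroup analyses. The same section promises that a detailed SAP will be published before analysis; it is not in the text supplied.

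Appendix 4 (renal substudy), under Statistical Analysis, has a related sentence: "Multivariate analysis will be performed adjusting for baseline imbalances and known covariates and confounders".

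**The concern.** Allocation is randomised 1:1, stratified by centre, so any baseline difference between arms arises by chance. A baseline p-value says nothing about whether a variable predicts death, yet prognostic strength largely determines whether adjusting for it matters. A rule that picks covariates by observed imbalance can bring in a variable with no bearing on mortality (Rhesus status, say) and leave out a strong predictor that happens to fall short of whatever cut-off is used.

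The primary test uses no patient covariates, and the only adjustment named in advance is for centre. This contingent analysis is therefore the only planned check of the primary result against differences in patient risk. If no imbalance is declared it is not run at all. If one is declared, the observed data decide the model.

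**Working it through.** **The plan's own figure.** The sample size for 28% versus 23.8%, two-sided alpha 0.05 and 90% power reproduces:

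- Uncorrected: n = [1.960 × √(2 × 0.259 × 0.741) + 1.282 × √(0.28 × 0.72 + 0.238 × 0.762)]² / 0.042² = 2,285 per group.
- With continuity correction: 2,332, as stated.
- With 5% added: 2 × 2,449 = 4,898, rounded up to 5,000.

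Nothing in this point changes that number.

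**Number of baseline tests.** The plan gives no count. From Data variables collected, 15 are readily testable:

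- age, gender, ABO group, Rhesus status, alloantibodies;
- prior heart disease, immunocompromise, active heart disease;
- APACHE III score, APACHE III diagnosis, SOFA at randomisation, haemoglobin at ICU admission;
- ventilation, renal replacement therapy and catecholamines at randomisation.

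Pre-transfusion haemoglobin, APACHE III risk of death and ethnicity (New Zealand only) would make 18. The count is an assumption, so a range is shown.

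**Chance of at least one p < 0.05 under correct randomisation.** For k independent tests this is 1 − 0.95^k:

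| k | Chance of at least one | Expected number |
|---|---|---|
| 5 | 22.6% | 0.25 |
| 10 | 40.1% | 0.50 |
| 15 | 53.7% | 0.75 |
| 18 | 60.3% | 0.90 |

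Several variables overlap (SOFA with organ support, for example), so independence overstates the figure. Simulating 15 equally correlated normal test statistics gives 50%, 46% and 36% for assumed correlations of 0.2, 0.3 and 0.5. A larger trial does not reduce these figures, because the false-positive rate does not depend on n.

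**The other reading of imbalance.** Suppose it means a material difference, for illustration 0.1 SD. At 2,500 per arm, z = 0.1 / √(2/2500) = 3.54 and p = 0.0004. Across 17 independent continuous variables the chance of any such difference is 1 − (1 − 0.0004)^17, about 0.7%. For comparison, p = 0.05 corresponds to only 1.96 × √(2/2500) = 0.055 SD.

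**What a missed covariate could amount to.** Take an imbalance at z = 1.9 (p about 0.057), which a 0.05 trigger would pass over, in a covariate with assumed correlation r = 0.1 to 0.4 with death. The standard error of the mortality difference at 2,500 per arm is √(2 × 0.259 × 0.741 / 2500) = 1.24 percentage points. The shift is r × 1.9 × 1.24, which is 0.24 points at r = 0.1 and 0.94 points at r = 0.4, against a target difference of 4.2 points. A fixed prognostic model would show such a shift; the planned rule would not.

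**The case against.** The strongest reply is that the plan never says p < 0.05 defines imbalance. That stands: the trigger is inferred from the tests named just before and the single threshold given just after. A reader might go further and infer that the plan is plainly wrong to call the event unlikely. The documents do not support that. Under a material-difference reading, with the illustrative cut-off of 0.1 SD, the event is rare (about 0.7%). What the text does support is that neither reading is stated. Without the 0.05 reading, imbalance has no criterion at all.

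A reader might also infer that the primary result is at risk. Take an unadjusted imbalance at p = 0.10, which is 1.645 × √(2/2500) = 0.0465 SD, in a covariate with an assumed odds ratio of 2 per SD. It shifts the log odds ratio by 0.0465 × ln 2 = 0.032, against a standard error of √(2 / (2375 × 0.26 × 0.74)) = 0.066 (26% mortality, 5% loss). That would move p = 0.05 to about 0.14 or 0.014. But this describes ordinary chance imbalance in an unadjusted estimate, present whatever the sensitivity model contains, and the unconditional type I error of the chi-square test already allows for it. The swing also depends on the assumed odds ratio and on starting exactly at 0.05.

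Nor does Appendix 4 simply repeat the rule. It also adjusts for known covariates and confounders, so prognostic variables are not left out merely because they look balanced. The residual problem there is that imbalance remains a selector and the known covariates are not named.

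Finally, the promised SAP could settle all this before unblinding. That is fair, and it makes the SAP the natural place for the change. But the present sentence is a stated method that the SAP would inherit, so this is more than missing detail. Admitting a non-prognostic variable at N = 5,000 would do little harm in itself; the cost lies in what is omitted.

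**Conclusion.** The point holds as a weakness in the sensitivity analysis, not as an error in the primary analysis. The covariate rule rests on an undefined imbalance, takes no account of prognostic strength, and makes the only check against patients' baseline covariates depend on the observed data. If the general 0.05 level is the trigger, at least one imbalance is expected in about 54% to 60% of correctly randomised trials of this kind (15 to 18 independent tests), or 36% to 50% for 15 correlated tests.

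These figures rest on the inferred trigger, the count of variables and the assumed correlations. The criticism that selection ignores prognosis rests on none of them. The chi-square test, the centre-adjusted model and the sample size are unaffected. The change should be made because the alternative is clearly better and uses data already collected.

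**What to change.** 1. Report baseline characteristics descriptively by arm and remove the baseline significance tests.
2. Replace the sentence on imbalances, and carry the replacement into the promised SAP. Suggested content: a sensitivity logistic regression for 90-day mortality, adjusted for centre and a list of covariates fixed before unblinding on prognostic grounds (for example age, APACHE III score and SOFA at randomisation), fitted whatever the observed balance.
3. In fixing the list, confirm that each covariate is measured before study blood is given. Patients may be enrolled in the emergency department, while APACHE III is recorded at ICU admission. State also how missing covariate values are handled.
4. In Appendix 4, drop baseline imbalances as a selector and name the known covariates.

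The sponsor's own observational study, described under Clinical significance, already adjusted for APACHE III and pre-transfusion haemoglobin, so candidates are at hand. The cost is wording only: no new data, and no change to the primary test or to N = 5,000.

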Only a large multicentre RCT can address whether the age of RBC transfusion affects mortality. Accordingly the TRANSFUSE study will have important health policy implications regardless of the outcome, in Australia and internationally.

OBJECTIVES

Aim

This study aims to determine whether, compared to standard care, transfusion of the freshest available allogeneic RBC decreases mortality of patients admitted to ICU.

Hypothesis

In critically ill patients who require a RBC transfusion, compared to standard practice, the administration of the freshest available compatible RBC reduces 90-day patient mortality.

STUDY OUTCOME MEASURES

Primary outcome

90 day mortality

Secondary outcomes

1. 28 day mortality
2. Persistent Organ Dysfunction combined with death at 28 [47]
3. Days alive and free of mechanical ventilation at day 28 post randomisation
4. Day alive and free of renal replacement therapy at day 28 post randomisation
5. Blood stream infection in ICU (post randomisation)
6. Length of stay in ICU and in hospital post randomisation
7. Proportion of patients who suffer at least one febrile non-haemolytic transfusion reaction in ICU
8. EQ-5D score at day 180 post randomisation [48]

OVERALL STUDY DESIGN

Study design

TRANSFUSE-RCT is a multi-centre, randomised, double blind, controlled trial, testing the effect of the freshest available RBC compared to standard practice, on mortality in critically ill patients who require RBC transfusion.

Study treatments

- Freshest available blood group: These patients will receive the freshest available group-specific compatible RBC unit in the transfusion service.
- Standard care group: These patients will receive standard practice, which is the oldest available group-specific compatible RBC unit in the transfusion service.

Study population

ICU patients or emergency department patients accepted for ICU admission in participating hospitals who meet all inclusion criteria and have no exclusion criteria. The study will enrol 5000 patients, in approximately 50 centres in Australia and New Zealand (ANZ).

Our observational study indicated that the recruitment of 40 patients per week is feasible and conservative [3]. At such a rate study recruitment would be completed in approximately 2.5 years. Allowing for study set up (12 months), 90 day outcome assessments, monitoring and analysis, a study time period of 4 years is anticipated.

Inclusion criteria

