ICU patients* with an anticipated ICU stay of at least 24 hours, in whom the decision has been made by medical staff to transfuse at least one RBC unit.

*A patient can be included into the study in the Emergency Department if the decision to admit the patient into the ICU has been taken.

Exclusion criteria

- Age younger than 18
- Previous RBC transfusion during the current hospital admission (including transfusion in another hospital for transferred patients)
- Diagnosis of transplantation or hematologic malignancy
- Pregnancy
- Cardiac surgery during the present hospital admission
- Expected to die imminently (<24hrs)
- The treating physician believes it is not in the best interest of the patient to be randomised in this trial.
- Known objection to the administration of human blood products
- Participation in a competing study (see below)

Co-enrolment

- Co-enrolment into any RBC transfusion studies is not permitted
- TRANSFUSE patients cannot be co-enrolled into the POLAR, ARISE, TRISS, and IRONMAN studies.
- Co-enrolment in the ADRENAL, EPO-TBI, PHARLAP, and SPICE studies is permitted by the TRANSFUSE management committee
- Co-enrolment in single site studies is permitted (excluding blood transfusion studies)

STUDY PROCEDURES

Eligible patients

Patients will be screened in the ICU and emergency department for their potential eligibility by the ICU research coordinator (RC) and clinicians. The ICU RC will place a sticker on the patient's chart to assist the ICU team with identifying eligible patients when a blood transfusion is ordered.

Enrolment

The inclusion and exclusion criteria will be checked when a clinical decision is made to transfuse. Transfusion indication, timing and number of the RBC units will be determined by the treating clinicians. However, we recommend following the current ANZ transfusion guidelines for ICU patients [49].

Randomisation

Randomisation will be performed by the ICU research staff using a Web-based computer system.

The patient will be allocated a unique study identification number at randomisation to identify their study involvement for the first and each subsequent RBC transfusion during their hospital stay. This number will be recorded on a sticker placed in the patient's chart and also on the RBC request form sent to the hospital transfusion service. The treatment allocation will be determined using variable block randomisation in a 1:1 ratio, stratified by centre.

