- Blood < 8 days old

Interim analysis

One planned interim safety analysis will be performed by the independent data and safety monitoring committee (DSMC) at 50% patient enrolment. It will examine safety and efficacy with stopping rules to be determined by the DSMC at their first meeting and to be published in the statistical analysis plan. Additionally an independent statistician will assess treatment separation by reviewing the average age of blood in the freshest and standard issue groups.

SAFETY

Data Safety Management Committee

An independent Data and Safety and Monitoring Committee (DSMC), comprising experts in clinical trials, biostatistics, transfusion medicine and intensive care medicine will be established before patient enrolment to review all trial protocols. The DSMC will conduct one planned interim safety analysis at half (2500) of the specified overall (5000) patient recruitment target, and will assess the differential proportion of all-cause mortality between the two treatment groups (a safety assessment of the trial primary outcome) as well as the differential cumulative “serious adverse events” reports. The DSMC may, in its absolute discretion, request assessment of any other trial data at any time.

Adverse events

Defined adverse events will be collected. Any undefined adverse events will be collected as free text bearing in mind that it is recognised that the patient population with critical illness and requiring RBC transfusions will experience a number of common aberrations in laboratory values, signs and symptoms due to the severity of the underlying disease and the impact of standard therapies. These will not necessarily constitute adverse events unless they are considered to be causally related to the study intervention or are otherwise considered to be of concern in the investigator’s judgement.

Serious adverse events

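### The under-8-days blood item is listed as an a priori subgroup, but it is an exposure set after randomisation largely by the allocated arm, so it cannot be a subgroup of the randomised comparison

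*Combined protocol and SAP*

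**What the plan says.** Under Statistical Considerations, Subgroup analyses, the protocol introduces its list with "A priori subgroup analyses will include" and gives three items: blood group O against non-O, illness severity by APACHE III and SOFA, and "Blood < 8 days old". The third has no further definition: no unit rule, no comparator and no time point.

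The Statistical and analytical plan says "This study will be analysed on an intention-to-treat basis", adds a supplementary per-protocol analysis, and promises more detail: "A detailed statistical analysis plan will be published prior to analysis being performed".

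On the blood itself:
- Exclusion criteria rule out "Previous RBC transfusion during the current hospital admission".
- Study treatments says of the freshest arm: "These patients will receive the freshest available group-specific compatible RBC unit in the transfusion service". The standard arm receives the oldest available compatible unit.
- Enrolment says "Transfusion indication, timing and number of the RBC units will be determined by the treating clinicians".
- Interim analysis says "an independent statistician will assess treatment separation by reviewing the average age of blood in the freshest and standard issue groups".

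**The concern.** A subgroup analysis of a randomised comparison needs a factor fixed before allocation, so that the arms remain comparable within each level. Blood group meets that condition. So does severity, if SOFA is the value at randomisation. Age of the blood received does not, because the arm assignment largely determines it.

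Two analyses could follow from the item as listed. Comparing the arms among patients given blood under 8 days old conditions on a consequence of allocation. Comparing those patients with patients given older blood is an as-received comparison. Neither is randomised. Because the item shares a list with baseline factors, its result could be given the same standing as theirs.

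**Working it through.** **Is the factor fixed before randomisation?**
1. Patients already transfused in this admission are excluded, so no enrolled patient has a trial unit, or a unit age, at baseline.
2. Under Randomisation, allocation comes first. The transfusion service then picks units from the freshest or the oldest stock according to arm.
3. Under Interim analysis, average age of blood is the measure of separation between arms. The arms are meant to differ on the variable that defines this item.
4. Under Blinding and in Appendix 1, the dates to be obtained are those of transfused units. No age of stock on hand at randomisation is listed.

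On the text, the item is therefore post-randomisation exposure. This needs no arithmetic.

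**What could follow if it were used as a subgroup?** The plan gives no figure to reproduce. The following is an illustration with no true effect of blood age.

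Inputs from the documents: mortality 28% (Sample size calculation), 2500 per arm, mean units *m* between 2 and 4.8 (general ICU range in Background).

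Assumed inputs, not in the documents: 20–50% of freshest-arm and 3–5% of standard-arm units are under 8 days; the number of units *N* is geometric with mean *m*; logit P(death) = *c* + *g* ln *N*, with *g* = 0.3 or 0.5 and *c* solved to give 28% overall; the death model is the same in both arms. Crossing *m* = 2, 2.5, 3.5, 4.8 with shares of 20, 35, 50% and 3, 5% and both slopes gives 48 scenarios.

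With *p* the chance that a unit is under 8 days, the probability of membership is *p*^*N* (all units), 1 − (1 − *p*)^*N* (any unit) or *p* (first unit). The 95% half-width is 1.96 × √[0.28 × 0.72 × (1/n₁ + 1/n₂)].

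Differences below are freshest minus standard mortality, in percentage points, with unit ages independent:

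| Rule | Freshest arm qualifying | Standard arm qualifying | Spurious difference | Half-width |
|---|---|---|---|---|
| All units | 5–33% | 0.6–2.6% | +0.3 to +2.9 | 11.4–23.4 |
| Any unit | 33–83% | 6–20% | −0.5 to −4.6 | 4.4–7.9 |
| First unit | 20–50% | 3–5% | 0 | 8.3–10.9 |

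Middle case (*m* = 3, shares 35% and 4%, *g* = 0.4), any-unit rule: averaging 1 − (1 − *p*)^*N* over the geometric gives *p* / [1 − (1 − 1/*m*)(1 − *p*)]. That is 0.35 / (1 − 0.6667 × 0.65) = 0.618, or 1544 patients, against 0.04 / (1 − 0.6667 × 0.96) = 0.111, or 278. Mortality within the subgroup is 30.1% v 32.1%, a spurious −2.0 points against a half-width of 5.7.

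First-unit rule: 2500 × 0.20 to 0.50 = 500 to 1250 patients, against 2500 × 0.03 to 0.05 = 75 to 125. The freshest arm supplies between 500/625 = 80% and 1250/1325 = 94% of the subgroup.

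**Dependence on independent unit ages.** Units issued together may be of similar age. Let a fraction *f* of patients have all their units in one age class, so membership becomes (1 − *f*) × rule + *f* × *p*:

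| *f* | All units, range | All units, middle case | Any unit, middle case |
|---|---|---|---|
| 0 | +0.3 to +2.9 | +1.3 | −2.0 |
| 25% | −0.04 to +0.95 | +0.34 | −1.9 |
| 50% | −0.15 to +0.44 | +0.08 | −1.7 |
| 100% | 0 | 0 | 0 |

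For the any-unit rule the full range at *f* = 50% is −0.4 to −4.0 points. Over *f* from 0 to 50% it is therefore about 0.4 to 4.6 points in favour of the freshest arm.

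**The case against.** Several points on the other side stand.

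- *A priori* means prespecified, not baseline. An analysis by blood received can be prespecified, and the plan already has a per-protocol analysis beside intention to treat. A reader might infer that the item contradicts the intention-to-treat statement; it does not. The fault lies in calling it a subgroup.
- The unit rule and comparator may properly wait for the promised SAP, so their absence is not the error. But every rule about transfused units is still post-randomisation.
- The item could be redefined as the age of the freshest compatible stock at randomisation, which would be a valid baseline factor. No section says this and no such data are planned.
- A reader might infer that the analysis will produce false harm or false benefit of a known size. The documents do not support that. The shares under 8 days, the unit-count distribution and the mortality slope are all assumed. The all-units harm depends on independent unit ages, and even then is at most 17% of its half-width.
- Nothing in the documents says the result will be presented as randomised evidence. That is a risk of the present list, not a stated intention.

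**Conclusion.** The concern holds in this limited form: as listed, the item is an exposure strongly affected by allocation, and it should not stand as a subgroup of the randomised comparison. That conclusion rests on the order of events in the protocol and on no assumed number.

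The size and direction of bias cannot be established from the documents. Under the stated assumptions only the any-unit rule gives a fairly robust distortion, towards false benefit in the freshest arm. The all-units rule is dominated by imprecision and its sign is uncertain once unit ages are correlated. The first-unit rule has no unit-count bias but is badly unbalanced. All unit-count biases are zero if mortality does not vary with number of units, and their signs reverse if mortality falls as units rise. The primary analysis and the sample size are not affected.

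**What to change.** Either of two changes is enough.

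1. Remove the item from the subgroup list. This is a protocol amendment, to be reported to the ethics committees.
2. Keep the analysis and state in the SAP: *Analysis by storage age of blood received (under 8 days) is not one of the subgroup analyses of the randomised comparison; this wording supersedes the protocol list. It is a prespecified exploratory analysis, not protected by randomisation. The unit rule, the comparator, the handling of patients who receive no unit, and the adjustment are fixed before unblinding.* Align the protocol list at the next amendment, so that the two documents do not disagree.

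Under the second option, add that number of units is itself measured after randomisation, so adjusting for it does not restore a randomised comparison.

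If a true subgroup is wanted, define it by a quantity fixed before randomisation, such as age of the freshest compatible stock at that time, and only if this can be obtained without extra data collection.

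The cost is small: the SAP is still to be published and the unit dates are already planned for collection. The downside is that the under-8-days result loses its subgroup status.

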The study will be conducted in the name of the TRANSFUSE investigators, the ANZIC RC and the ANZICS CTG. The central project coordination and data management will be provided by the ANZIC RC at Monash University, Melbourne. The principal publication from the study will be in the name of the TRANSFUSE Investigators with full credit assigned to all collaborating investigators, research coordinators and institutions. Where an individuals' name is required for publication it will be that of the writing committee, with the chair of the writing committee listed first and subsequent authors listed alphabetically.

Funding bodies will be acknowledged in the publication.

RESEARCH TIMELINES

Time frame indicator	Milestone
February 2012	Appoint Project Manager
March 2012	Protocol & HREC approval (Monash University)
April –Aug 2012	CRF & database development
April – Sept 2012	Staff training & ethical approval at collaborating sites
Oct 2012	Commence recruitment
Jan 2015	Complete 50% recruitment
Mar 2015	Interim analysis
Aug 2016	Complete 100% recruitment
Nov 2016	Complete 90 day follow up
Jan 2017	Query resolution & database lock of primary endpoint data
Feb 2017	Complete 180 day follow up
Mar 2017	Query resolution and database lock of secondary endpoint data
April 2017	Primary manuscript submitted

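### Is the single interim analysis unsound because it is dated two months after half recruitment, while the primary outcome is 90-day mortality, and because it is called both a safety and an efficacy look?

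*Combined protocol and SAP*

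**What the plan says.** The plan describes the interim in two places in the combined protocol.

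- **Statistical considerations, Interim analysis.** One look at 50% enrolment, introduced as a safety analysis. The next sentence reads: "It will examine safety and efficacy with stopping rules to be determined by the DSMC at their first meeting". The rules are then to be published in the statistical analysis plan.
- **Safety, Data Safety Management Committee.** "The DSMC will conduct one planned interim safety analysis at half (2500) of the specified overall (5000) patient recruitment target". The committee "will assess the differential proportion of all-cause mortality between the two treatment groups (a safety assessment of the trial primary outcome"), together with serious adverse event reports. It may ask for any other trial data at any time, and it is to be set up before patients are enrolled.

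The Statistical and analytical plan section defines the outcome and the final test: "The primary outcome, 90 day all-cause mortality will be analysed using a Chi-square test statistic", and "A two-sided p-value of 0.05 will be considered to be statistically significant".

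The Research timelines table works in whole months. It enters "Complete 50% recruitment" at January 2015 and the interim at March 2015. At the end of the trial, recruitment closes in August 2016, "Complete 90 day follow up" stands at November 2016 and "Query resolution & database lock of primary endpoint data" at January 2017.

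**The concern.** Two things look wrong on a first reading.

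The first is the calendar. The interim mortality comparison is tied to the primary outcome, which needs 90 days, yet the table leaves about two months between the 2,500th patient and the look. For the same outcome at the end of the trial the table allows five months, August 2016 to January 2017. If 90-day mortality were needed for all 2,500, the late patients would have to be left out or counted with incomplete follow-up, and the plan does not say which.

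The second is purpose. A look for harm alone leaves the error rate for a claim of benefit intact. A look that can stop for benefit spends some of the 0.05, so the final level should be lowered to match. With safety named in one sentence and safety plus efficacy in the next, a reader may wonder which kind of look is planned and whether a final two-sided 0.05 is still correct.

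**Working it through.** **Plan's own figure.** Inputs from Sample size calculation: 28% against 23.8%, two-sided 0.05, power 90%. With mean proportion 0.259 and difference 0.042:

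n = [1.960 × √(2 × 0.259 × 0.741) + 1.282 × √(0.28 × 0.72 + 0.238 × 0.762)]² / 0.042² = 2,284.3

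The continuity correction, (n/4) × [1 + √(1 + 4/(0.042n))]², gives 2,331.7, so 2,332 per group, as stated. The interim question does not touch this figure.

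**Follow-up of the 2,500th patient.** The days within each month are not given, so I take the extremes.

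- Shortest: 31 January to 1 March 2015 = 29 days.
- Longest: 1 January to 31 March 2015 = 89 days.

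Day 90 is therefore out of reach for that patient by 1 to 61 days. Day 28 is reached in every case.

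**Patients short of day 90.** Average rate over the first half, starting in October 2012:

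- Best case: 2,500 / 822 days = 3.04 per day; 1 day × 3.04 = 3 patients (0.1%).
- Both milestones mid-month, start 1 October: 2,500 / 836 = 2.99 per day; 31 days × 2.99 = 93 (3.7%).
- Worst case: 61 days at 2.93 per day (start 1 October 2012) = 179, or at 3.04 per day (start 31 October) = 186 (7.4%).

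If recruitment in late 2014 had already reached the average planned for the second half (2,500 in 19 months, about 4.33 per day), 61 × 4.33 = 264 (10.6%). That applies a later rate to an earlier period, so I treat it as an outer bound.

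**If late patients are left out.** Information fraction = (2,500 − short) / 5,000: 0.499 for 3 patients, 0.463 for 186, 0.447 for 264. The standard error of the risk difference, √(4 × 0.259 × 0.741 / n), is 0.0175 at n = 2,500, 0.0182 at 2,314 and 0.0185 at 2,236. At the outer bound it is about 6% larger.

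**If late patients are counted on deaths known so far.** Assume the deaths still to come are the gap between 25% hospital mortality and the estimated 28% at 90 days, that is 3 percentage points. Uncounted deaths: 0.03 × 93 = 3, 0.03 × 186 = 6, 0.03 × 264 = 8. Expected deaths in 2,500 are 0.259 × 2,500 = 648, so 8 is 1.2%. Doubling the assumed gap gives 16, or 2.4%. The same cut-off applies in both arms.

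**Final significance level.** The plan states no boundary, so this is conditional. Suppose benefit could stop the trial and the final test stayed at 0.05. Treating the two test statistics as bivariate normal with correlation √t, the overall two-sided error for interim thresholds of 0.001, 0.00305 and 0.0052 is:

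| Information fraction t | 0.001 | 0.00305 | 0.0052 |
|---|---|---|---|
| 0.50 | 0.0502 | 0.0510 | 0.0520 |
| 0.447 | 0.0503 | 0.0512 | 0.0523 |

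Under a harm-only rule the error for a claim of benefit is not inflated. If an O'Brien-Fleming-type rule were adopted with its matching final level of 0.0490, the requirement would rise from 2,332 to 2,344 per group. That is still below the 0.95 × 2,500 = 2,375 expected after 5% loss.

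**The case for a change.** The best case for acting is that the plan does name the primary outcome for this look, that no day in March 2015 gives every one of the 2,500 a 90-day result, and that no section states the time point, the analysis set or the data cut. Someone must choose, and that choice should be made before unblinded data are seen. The scope of the look also bears on the final 0.05, and a sentence or two would settle both matters at no cost in patients or time.

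The dates are right, and the silence on the analysis set is real. The rest does not carry. The trigger is enrolment, and the committee section speaks of all-cause mortality without a day count. The 90 days enter through the bracketed reference to the primary outcome, and the requirement that all 2,500 reach it is nowhere in the text. A comparison among those with 90-day status, or of deaths known at the cut, satisfies the wording. The five months at the end of the trial include a database lock, which the plan does not ask of the interim.

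On purpose, the efficacy sentence itself sends the stopping rules to the committee's first meeting and then to the published analysis plan. Whether benefit can stop the trial is one of those rules, so it has been assigned to a named body and document. Larger inflation, such as 0.083 from testing twice at 0.05, needs a liberal benefit rule and an uncorrected final level, neither of which the plan states.

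**Conclusion.** No change follows. The two sections and the timeline can be read together: an enrolment-triggered look, reported about two months later, with incomplete 90-day follow-up in the last patients recruited. The missing detail is an analysis set and data cut, which a monitoring committee's statistician defines as a matter of course. The committee can also request further data whenever it wishes. The two descriptions of purpose are compatible, because in this trial a mortality difference is evidence on safety in one direction and on efficacy in the other.

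The stakes are small on any reasonable choice: 0.1% to 7.4% of the 2,500 short of day 90 at the first-half rate, 10.6% at the outer bound; an information fraction of 0.447 or more; and about 8 of 648 deaths uncounted at that bound. With a strict benefit boundary and no correction, the overall error would be 0.0502 to 0.0523.

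These figures rest on assumed days within the stated months, even recruitment within each half, and late deaths equal to the gap between hospital and 90-day mortality. The error rates also assume a boundary, since the plan defers it.
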